2.2.5. Pharmacodynamics (PD) Analysis Set

The PD analysis set is defined as all subjects in the PK analysis set for whom at least one PK parameter could be derived.

2.3. Definition of Subgroups

See [Table 6](#) for the definitions of all the subgroups. The third column in the table indicates for which endpoints the subgroup is applied.

Descriptive statistics will be produced for the different subgroups.

In demographics and baseline disease characteristics, the following subgroups will be used:

- Region
- Influenza A subtype category
- Age group
- Time since onset of influenza symptoms (actual)
- Type of SOC at baseline (actual)
- Influenza season
- Study period
- Baseline resistance
- Any baseline polymorphism
- COVID-19 impacted

Stratification factors (actual) will be used as subgroups for concomitant medication.

For the primary and two most important secondary endpoints (ie, 'Incidence of treatment-emergent adjudicated influenza complications' and 'Incidence of hospital admission 28 days after treatment initiation') the subgroup with subgroup*treatment interaction term will be added in the statistical analysis models, except for the study period subgroup, where the analysis will be performed separately for each individual category of the subgroup. For further details see Section 5.2.3 and Section 5.3.2. For other endpoints, the statistical analysis will be performed separately for each individual category of the subgroup.

Table 6: Subgroups with their definition

Subgroup	Definition	Endpoints
Region	Based on country according to UN classification of Geographic regions ^[5] : 
 • Europe/Africa • Northern-America • Latin America and the Caribbean • Asia and Oceania 	- Efficacy (primary and secondary endpoints, excluding viral kinetics endpoints)
Age group (years)	
 • 13-17 years • 18-65 years • 66-85 years 	- Efficacy (primary and secondary endpoints, excluding viral kinetics endpoints) - All safety
Type of SOC at baseline (actual)	
 • SOC including influenza antiviral treatment • SOC not including influenza antiviral treatment 	- All efficacy - Viral phenotype - Viral genotype - Safety (AE summary, AEs and SAEs by MedDRA system organ class and preferred term, influenza-related complications, laboratory toxicity)
Time (hours) from onset influenza symptoms to	
 • ≤48 hours • >48 hours 	- All efficacy - Viral phenotype - Viral genotype

Subgroup	Definition	Endpoints
first study drug intake (actual)		
Influenza A subtype category	
 • A/H1N1 • A/H3N2 • Other 	
 - Efficacy (primary and two most important secondary endpoints only) - All viral kinetics - Viral phenotype - Viral genotype
Baseline polymorphism (based on influenza PB2 genotype)	Polymorphism on one or any of these amino-acid positions of interest: 
 • Q306 • F323 • S324 • F325 • S337 • H357 • F363 • K376 • T378 • F404 • Q406 • M431 • N510 	
 - Efficacy (primary endpoint only) - All viral kinetics - Viral phenotype - Viral genotype
Baseline resistance (based on influenza PB2 phenotype)	Based on fold change (FC) in EC ₅₀ for pimodivir: 
 • FC ≤4 • FC >4 	
 - Efficacy (primary endpoint only) - All viral kinetics - Viral phenotype - Viral genotype
Baseline Fever	Baseline (temperature ≥37.0°C) as recorded as part of the vital signs assessment	- Resolution of fever only
Influenza season	
 • Northern Hemisphere 2017/2018 • Southern Hemisphere 2018 • Northern Hemisphere 2018/2019 • Southern Hemisphere 2019 • Northern Hemisphere 2019/2020 • Southern Hemisphere 2020 and so on, to capture all enrolled subjects	
 - Efficacy (primary and two most important secondary endpoints only) - All viral kinetics - Viral phenotype - Viral genotype
Study period	
 • Pre interim (subjects enrolled for the interim analysis, ie randomized before or on February 28, 2020) • Post interim (subjects enrolled after the interim analysis, ie randomized after February 28, 2020) 	
 - Efficacy (primary and two most important secondary endpoints only) - Safety (AE summary, AEs and SAEs by MedDRA system organ class and preferred term, influenza-related complications, laboratory toxicity)
COVID-19 impacted	
 • Yes • No 	
 - Efficacy (primary and two most important secondary endpoints only) - Safety (AE summary, AEs and SAEs by MedDRA system organ class and preferred term, influenza-related complications, laboratory toxicity)

Influenza season is defined as follow:

Subjects enrolled from 1st October 2017 to 31st March 2018 are considered to be in the Northern Hemisphere 2017/2018 category and subjects enrolled from 1st April 2018 to 30th September 2018 are considered to be in the Southern Hemisphere 2018 category. Subjects enrolled from 1st October 2018 to 31st March 2019 are considered to be in the Northern Hemisphere 2018/2019 category and subjects enrolled from 1st April 2019 to 30th September 2019 are considered to be in the Southern Hemisphere 2019 category, and so on.

A subject is considered to be impacted by the COVID-19 pandemic if they experienced at least one of the following:

- discontinued from the study (or study drug) due to COVID-19
- had a COVID-19 related AE
- had a COVID-19 related protocol deviation (major or minor)

Additional subgroup analysis may be specified in a separate analysis plan and reported separately from the clinical study report.

2.4. Study Day and Relative Day

Reference date refers to the start date of the first study drug administration. All efficacy and safety assessments at all visits will be assigned a day relative to this date.

The relative day (*reldy*) will be defined as:

$reldy = visit\ date - reference\ date + 1$ for visits on or after the reference date,

$reldy = visit\ date - reference\ date$ for visits before the reference date.

Consequently there is no 'day 0' defined.

2.5. Baseline and Endpoint

The baseline analysis visit is defined as the last assessment before the first intake of the study drug, with the possible exception for height, weight, and virology results from central lab testing. Height and weight are only recorded once, at the screening/baseline visit, and the values recorded at this visit will be allocated to the baseline analysis visit irrespective of start of study drug. For the virology parameters, if no measurement is available prior to first dose of study drug, then the first result from central lab testing obtained up to and including 30 minutes after first dose of study drug will be considered as the baseline assessment and will be flagged in the analysis dataset.

As specified in the protocol, an ECG recording within 1 calendar day before signing of the informed consent form (ICF/assent form) can be used as baseline ECG requirement, if no ECG measurement was performed between signing ICF and first study drug intake.

For programming purposes, the baseline record will be doubled in the ADAM datasets, the doubled record will be renamed with AVISIT = 'Baseline', AVISITN = 0 and will be assigned to the treatment phase.

For viral phenotyping, the last visit (Endpoint) is defined as the last study visit/timepoint for which an EC₅₀ and/or IC₅₀ result is available (including unscheduled visit results).

For vital signs, ECG and central laboratory data the last study visit (Endpoint) is defined as the last scheduled study visit/timepoint and will be either the final study visit (at Day 28) or the safety follow-up visit.

2.6. Other Definitions

For FDA marketing authorization approval in the US all subjects will be included in the analysis.

The oseltamivir subset (OST subset) contains only those subjects whose SOC treatment contains oseltamivir (OST). The first dose of OST may be given before the subject was randomized but should be started no later than Day 2 morning (up to noon). The complete analysis will be repeated restricted to the OST subset to support marketing authorization approval in EMA.

Analyses to support authorization approval in other regions or countries will include all subjects unless the Health Authority of the region or country requests otherwise and may be specified in a separate analysis plan and may also be reported separately.

3. INTERIM ANALYSIS AND DATA MONITORING COMMITTEE REVIEW

3.1. Interim Analysis

An interim analysis will be implemented to re-estimate the study sample size and to perform an assessment of futility. The maximum total number of subjects that may be enrolled in the study will be approximately 1,080. This interim analysis will be implemented through an IDMC, providing recommendations to a Sponsor Committee. Only the IDMC and the independent Statistical Support Group will be unblinded to the data. Details will be specified in the IDMC charter.

Details on the statistical decision rules will be provided in the IDMC SAP. The interim analysis will be conducted at the end of the first influenza season when between 360 and 540 subjects have been enrolled or during the season when 540 subjects have been enrolled. Further details will be specified in the IDMC charter.

3.2. Independent Data Monitoring Committee

An IDMC will be established to monitor data on a regular basis. The committee will meet periodically to review interim data. After the review, the IDMC will make recommendations regarding the continuation of the study. The details will be provided in a separate IDMC charter.

The IDMC will consist of at least 3 members, including one medical expert in the relevant therapeutic area and at least one statistician knowledgeable about statistical methods for clinical studies and sequential analysis of study data. One of these individuals will chair the Committee. The IDMC responsibilities, authorities, and procedures will be documented in its charter.

4. SUBJECT INFORMATION

All general analyses will be done on the ITT-i Set and the Safety Set unless specified otherwise for a specific display.

4.1. Demographics and Baseline Characteristics

Demographics and baseline disease characteristics will also be done on the PP and ITT-ni sets.

Descriptive statistics or frequency tabulation will be provided for the following parameters.

- Demographic parameters:
 - Sex (Male, Female)
 - Race (White, Black or African American, Asian, American Indian or Alaska Native, Native Hawaiian or Other Pacific Islander, Multiple). The specification of the category 'Multiple' will only be listed. The 'Not reported' category will not be added for the denominator.
 - Ethnicity (Hispanic or Latino, Not Hispanic or Latino)
 - Country
 - Geographic region (Based on country according to UN classification of Geographic regions^[5]: Europe/Africa, Northern-America, Latin America and the Caribbean, Asia and Oceania)
 - Age (years and categories: 13-17 years [≥ 13 - < 18], 18-65 years [≥ 18 - ≤ 65], 66-85 years [> 65 - ≤ 85])
 - Age (years and categories: Adolescents (12-17 years) [≥ 12 - ≤ 17], Adults (18-64 years) [≥ 18 - ≤ 64], From 65 to 84 years [≥ 65 - ≤ 84], 85 years and over [≥ 85])
 - Weight at baseline (kg)
 - Height at baseline (cm)
 - BMI at baseline = Weight at baseline (kg) / (Height at baseline (m))² (rounded to 1 decimal. Although available in the raw data, BMI will be recalculated from last weight and height measurement before start of treatment)
 - Current Tobacco use: tobacco, cigarettes, cigars, patches/gum, pipes, E-cigarettes or equivalent, smokeless tobacco (Yes, No, Missing) Note that 'No' also includes ex-smokers
 - Childbearing potential (only listed)

- Baseline disease characteristics:
 - Influenza A subtype category (A/H1N1, A/H3N2, other)
 - Baseline influenza A viral load (log₁₀ vp/mL), assessed by qRT-PCR
 - Baseline influenza A viral titer (log₁₀ TCID₅₀/mL) assessed by viral culture
 - Broad respiratory panel (show the reported pathogen)
 - Baseline composite symptom score of 10 influenza-related symptoms
 - Return to daily activities questionnaire baseline category

- Patient Global Impression of Severity of Influenza symptoms at baseline
- EQ-5D VAS at baseline
- EQ-5D Valuation index at baseline
- Respiration rate at baseline (breaths/min)
- Heart rate (beats/min)
- Temperature (°C) at baseline
- qRT-PCR negativity at baseline
- Viral culture negativity at baseline
- Time since onset of influenza symptoms, as randomized (≤ 48 hours, > 48 hours)
- Time since onset of influenza symptoms, actual time (hours) [the actual time will be calculated from start date and time of acute respiratory symptoms until datetime of first study drug intake, if the time is missing, the midpoint of the time interval as recorded per CRF will be used]
- Time since onset of influenza symptoms, actual time (≤ 48 hours, > 48 hours)
- Type of SOC at baseline, as randomized (including or not including antiviral treatment),
- Type of SOC at baseline, actual (including or not including antiviral treatment), for the SOC including antiviral treatment the influenza antiviral will also be shown.
- SOC including oseltamivir (yes, no)
- Type of influenza A diagnostic assay (Rapid antigen-based diagnostic test, Rapid molecular diagnostic test)
- Baseline resistance
- Any baseline polymorphism

4.2. Disposition Information

Summaries will be provided for the following disposition information:

- Number of subjects screened, screening failures, randomized, randomized and not treated, randomized and/or treated, randomized and treated, randomized and no confirmed influenza A, ITT-i set, ITT-ni set, per protocol set, and safety set. The planned treatment arm will be shown, except for the randomized and/or treated and safety sets where the actual treatment will be shown. For the ITT-i, ITT-ni, per protocol and safety analysis sets the number (%) of subjects within that set impacted by the COVID-19 pandemic will also be presented.
- Number of subjects who completed/discontinued treatment and/or the trial, with the reasons of discontinuation.
- Kaplan-Meier curves of the time to completion or discontinuation (in days) of the treatment/trial per treatment group. Note at the final analysis all subjects will have completed or discontinued the treatment/trial and no subjects will be censored.
- Number of subjects with a visit at each scheduled analysis time point by phase.
- Number of subjects enrolled per month, quarter, season, and year of enrolment

4.3. Treatment Compliance

Treatment compliance for pimodivir/placebo is calculated as the actual number of doses taken, as a percentage of the planned number of doses. The actual number of doses taken will be derived from the drug accountability information (DA domain) as the difference between the amount of drug dispensed and the drug returned (in case both amounts are known), otherwise treatment compliance will be missing.

For placebo or pimodivir this number needs to be divided by 2 as the study uses 300 mg tablets. The planned number of medication is 20 tablets of placebo or pimodivir hence the planned number of doses per medication equals 10 doses. Note that the planned number of doses is irrespective of whether the subject discontinued during the treatment phase.

Dosing compliance will be summarized descriptively in the treatment phase and by discontinuing the trial during the treatment period (Yes, No).

4.4. Extent of Exposure

The extent of exposure (hours) is defined as datetime of last study drug intake – datetime of first study drug intake + 12 hours. Note: treatment interruptions will not be taken into account.

Extent of exposure will be summarized descriptively in the treatment phase.

4.5. Protocol Deviations

The number and percentage of subjects with major protocol deviations will be tabulated overall and per coded major protocol deviation.

A listing will be made of all major protocol deviations and separately for major protocol deviations related to COVID-19 for the subjects in the safety set.

A listing will be made of minor protocol deviations related to COVID-19 for the subjects in the safety set.

Additionally, for subjects in the ITT-i set, the number and percentage of subjects with a reason for exclusion from the per protocol set will be tabulated overall and for each reason for exclusion (see Section 2.2.2.2)

A listing will also be made of all reasons for exclusion from the per protocol set for subjects in the ITT-i set.

4.6. Prior and Concomitant Medications

Medications reported from 7 days before first dose of study drug and up to last contact date will be summarized by preferred term using the World Health Organization-Drug Dictionary for the ITT-i Set and the Safety Set as frequency tables in 2 parts:

1. Prior medication: medication that started before the first dose of study drug, regardless of when dosing of the medication ended

2. Concomitant medication: medication received at or after the first dose of study drug, medication that was received before initial dosing and continued after initial dosing of study drug, or medication with missing stop date.

(Medication that started before the first dose of study drug and continued after the first dose of study drug will be summarized as prior medication and separately as concomitant medication.)

A frequency tabulation of concomitant medication will be shown by Anatomical Therapeutic Chemical (ATC) class level up to level 3. Frequency tabulations will be made for concomitant antibiotics, type of SOC, corticosteroids, and medication administered to treat COVID-19 infection by ATC class. Additionally, tabulations will be made of concomitant corticosteroids and antibiotics administered because of adverse events reported as influenza complications.

The ATC level 2 code J01 will be used to identify concomitant antibiotics.

The ATC level 2 code H02 and the ATC level 4 codes M01BA, R03BA, and R03AK will be used for identifying corticosteroids.

Separate frequency tabulations will be made for antipyretic medication. The ATC level 3 codes N02BA and N02BE and the generic medication names paracetamol, ibuprofen, and acetylsalicylic acid will be used to identify antipyretic medications.

If a prior/concomitant therapy record misses components of its start and/or stop dates (time and/or day and/or month and/or year), the following actions will be taken:

1. In case of partial start or stop date/times, the concomitant therapy records will be allocated to prior and/or concomitant using the available partial information, without imputations.
2. In case of a completely missing start date, the prior and/or concomitant therapy will be considered as having started before the trial.
3. In case of a completely missing end date, the prior and/or concomitant therapy will be considered as ongoing at the end of the trial.

4.7. Medical history

The influenza vaccination status will be tabulated by:

- Vaccinated in previous season, not in current season
- Vaccinated in current season, not in previous season
- Vaccinated in previous and current season.
- Not vaccinated in previous and current season

The use of antiviral influenza medication prior to the study drug initiation will be tabulated separately.

Influenza history will be listed, including information on first acute respiratory symptoms, influenza vaccination status and previous antiviral influenza therapy.

Other medical history will be tabulated by subcategory and/or will be listed.

5. EFFICACY

Descriptive statistics will be used for all efficacy endpoints and will be tabulated by treatment arm and stratification factors (baseline SOC and time since onset of symptoms). For the analyses restricted to subjects who received OST as part of their SOC, type of baseline SOC will not be included as a stratification factor or model parameter.

5.1. Analysis Specifications

5.1.1. Level of Significance

As a confirmatory strategy, to account for multiplicity in the statistical evaluation of the most important efficacy endpoints, hierarchical testing will be applied to control for overall Type I error. The following endpoints are included in the confirmatory strategy:

Primary Endpoint

- Time to resolution of the 7 primary influenza-related symptoms (cough, sore throat, headache, nasal congestion, feeling feverish, body aches and pains, fatigue)

Secondary Endpoints

- Incidence of complications associated with influenza after the start of study treatment
- Hospital admission rates 28 days after treatment initiation

First, the primary endpoint will be tested for superiority of pimodivir in combination with SOC over placebo in combination with SOC at the 2-sided 5% significance level. If superiority is shown on the primary endpoint, the first secondary endpoint in the sequence as indicated above will be tested for superiority at the same significance level. If superiority is shown for this secondary endpoint, the second (and last) secondary endpoint in sequence will be tested. In case superiority is not shown for an endpoint, no further endpoints in the sequence will be tested for superiority.

This testing procedure will be applied on the ITT-i set.

The final analysis on the ITT-i set (to support FDA marketing authorization approval) and the final analysis on the OST subset (to support marketing authorization approval in EMA) will be performed independently, using a 5% two-sided significance level for each.

Statistical Methodology for Evaluation at the Final Analysis

The p-values for the final analysis of the primary endpoint and the two most important secondary endpoints will be based on an inverse-normal combination test. For the primary endpoint, the p-values are obtained from the Gehan-Wilcoxon test. For incidence of complications associated with influenza after the start of study treatment and Hospital admission rates 28 days after treatment initiation the p-values will be obtained from a logistic regression model (see Sections 5.3.2 and 5.3.2.2).

All p-values below are one-sided p-values, to evaluate rejection of the null hypothesis that pimodivir is not better than placebo.

Let:

- p = p-value from the analysis of the ‘pre interim’ category of the ‘study period’ subgroup
- q = p-value from the analysis of the ‘post interim’ category of the ‘study period’ subgroup
- N_1 = actual sample size at interim, ie the number of subjects in the ‘All randomized analysis set (RAND)’ included in the interim analysis.
- N = per-protocol sample size (=720)
- $w_1 = \text{sqrt}(N_1/N)$
- $w_2 = \text{sqrt}(1-(N_1/N))$
- $\phi^{-1}(x)$ the inverse of the standard normal cumulative distribution function in x

The p-values resulting from the following combination test should be below the pre-specified alpha to claim superiority:

$$1 - \phi(C(p,q)), \text{ where } C(p,q) = w_1 * \phi^{-1}(1-p) + w_2 * \phi^{-1}(1-q)$$

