**Table 2: Estimates of Intercept and Scale Parameter From Study 63623872FLZ2001**

Model	Parameter	Estimate	95% CI
Log-logistic	Intercept	3.8546	(3.2000, 4.5092)
	Scale	0.5213	(0.4633, 0.5867)
Log-normal	Intercept	3.6277	(2.8897, 4.3656)
	Scale	0.9880	(0.8919, 1.0945)

For a trial with a sample size of 600 patients, recovery times were simulated based on the log-logistic model and separately also based on the log-normal distribution, assuming that the time to recovery is reduced by 25% in the pimodivir with SOC treatment arm compared to the placebo with SOC treatment arm, and that the subjects are randomized in a 1:1 ratio between the 2 treatment groups. To consider the variability in the intercept and scale parameters, the simulated recovery times were derived using the estimate of each parameter and using the upper limit of the 95% CI for each parameter. A trial was simulated 10,000 times.

The Gehan-Wilcoxon test, log-logistic AFT model, and log-normal AFT model were used to analyze each of the 10,000 simulated datasets, for each recovery time distribution (log-logistic, log-normal) and for each parameter estimate (estimate, upper limit of the 95% CI). The power, for each statistical test, was estimated as the number of datasets where the 1-sided p-value from the test was <0.025 out of the 10,000 simulated datasets.

**Table 3** provides the estimates of power for each statistical test and simulated time to resolution of influenza symptoms distributions.

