For a trial with a sample size of 600 patients, recovery times were simulated based on the log-logistic model and separately also based on the log-normal distribution, assuming that the time to recovery is reduced by 25% in the pimodivir with SOC treatment arm compared to the placebo with SOC treatment arm, and that the subjects are randomized in a 1:1 ratio between the 2 treatment groups. To consider the variability in the intercept and scale parameters, the simulated recovery times were derived using the estimate of each parameter and using the upper limit of the 95% confidence interval (CI) for each parameter. A trial was simulated 10,000 times.

The Gehan-Wilcoxon test, log-logistic AFT model, and log-normal AFT model were used to analyze each of the 10,000 simulated datasets, for each recovery time distribution (log-logistic, log-normal) and for each parameter estimate (estimate, upper limit of the 95% CI). The power, for each statistical test, was estimated as the number of datasets where the 1-sided p-value from the test was <0.025 out of the 10,000 simulated datasets.

Table 2 provides the estimates of power for each statistical test and simulated time to resolution of influenza symptoms distributions.

Table 2: Estimated Power From 3 Statistical Tests

Simulated Distribution of Recovery Time	Estimated Power (%)		
	Gehan-Wilcoxon	AFT Log-logistic Model	AFT Log-normal Model
Log-logistic (estimate)	97.3	97.3	96.2
Log-logistic (upper CL)	93.3	93.4	91.3
Log-normal (estimate)	93.7	94.2	94.8
Log-normal (upper CL)	88.3	89.1	89.6

For the simulated recovery times based on the log-logistic model, the estimated power was greater than 90% when using both the estimate and the upper limit of the 95% CI for the intercept and scale parameter from the Phase 2 study.

For the simulated recovery times based on the log-normal model, the estimated power was greater than 90% and greater than 85% when using the estimate and the upper limit of the 95% CI, respectively, for the intercept and scale parameters from the Phase 2 study.

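### Does judging a one-sided combination p-value against an unnumbered alpha double the false-positive rate?

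*SAP*

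**What the plan says.** SAP 5.1.1 sets up a three-step hierarchy: the primary endpoint, then influenza complications, then hospital admission. The primary comparison tests superiority "over placebo in combination with SOC at the 2-sided 5% significance level", and each later step uses the same level. The ITT-i analysis and the oseltamivir-subset analysis "will be performed independently, using a 5% two-sided significance level for each".

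The section then describes the final test. It introduces the p-values with "All p-values below are one-sided p-values, to evaluate rejection of the null hypothesis that pimodivir is not better than placebo", combines the pre-interim value p and the post-interim value q as C(p,q), and closes with "The p-values resulting from the following combination test should be below the pre-specified alpha to claim superiority". The combined p-value is 1 − Φ(C). The weights are w1 = √(N1/720) and w2 = √(1 − N1/720), where N1 is the number randomized and included in the interim analysis.

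A numerical one-sided cut-off does appear in both documents, in the sample-size sections. SAP 1.4 defines power through "the number of datasets where the 1-sided p-value from the test was <0.025 out of the 10,000 simulated datasets", and Protocol 11.3 uses the same criterion: "the 1-sided p-value from the test was <0.025 out of the 10,000 simulated datasets".

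**The concern.** The decision sentence puts a one-sided statistic beside a level that the section expresses only on a two-sided scale, and it gives neither the converted number nor a cross-reference. A reader who looks in SAP 5.1.1 for a figure to insert finds 5% and nothing else. Used as it stands, that figure gives superiority at one-sided p < 0.05, which is a two-sided 10% test.

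The sentence matters more than most. It decides the primary endpoint, which gates both key secondary endpoints, and it is applied again in the oseltamivir subset. If 0.05 really were the rule, the 5% two-sided control claimed in the same section would not hold. A threshold argued over after unblinding would also no longer count as pre-specified.

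**Working it through.** **1. What the stated level implies.** A two-sided 5% test allows 0.05 / 2 = 0.025 in each direction. Superiority at that level means one-sided p < 0.025, that is, C > 1.960. A cut-off of 0.05 (C > 1.645) arises only if the two-sided label, attached to the level both times it is stated, is dropped.

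**2. Which cut-off the plan's own figures use.** Inputs from SAP 1.4:
- 600 analysed subjects, 1:1
- 25% reduction in time to recovery, so |ln 0.75| = 0.2877
- log-logistic scale 0.5213 (upper limit 0.5867)
- log-normal scale 0.9880 (upper limit 1.0945)

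Wilcoxon normal approximation, with √(600/4) = 12.247:
- log-logistic: power = Φ(0.2877 × 12.247 / (scale × √3) − z)
- log-normal: power = Φ(0.2877 × 12.247 × √(3/π) / scale − z)

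where z = 1.960 for one-sided 0.025 and z = 1.645 for one-sided 0.05. For the first row, 0.2877 × 12.247 / (0.5213 × 1.732) = 3.902, and Φ(3.902 − 1.960) = 97.4%.

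| Scenario | SAP Table 2, Gehan-Wilcoxon | One-sided 0.025 | One-sided 0.05 |
|---|---|---|---|
| Log-logistic, estimate | 97.3% | 97.4% | 98.8% |
| Log-logistic, upper limit | 93.3% | 93.4% | 96.6% |
| Log-normal, estimate | 93.7% | 93.6% | 96.7% |
| Log-normal, upper limit | 88.3% | 88.2% | 93.3% |

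A simulation of 10,000 trials per scenario (Gehan test, censoring at 28 days = 672 h) gave the same four values at 0.025. At 0.05 the formula exceeds the stated figures by 1.5, 3.3, 3.0 and 5.0 points. Even the smallest gap is not simulation noise: with 10,000 replicates the standard error at 97.3% is √(0.973 × 0.027 / 10,000) = 0.16 points, so 1.5 points is about nine standard errors. The power table was built on one-sided 0.025.

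**3. What each reading would do.** Under the null the stage-wise z-values are independent standard normals, and w1² + w2² = N1/720 + (1 − N1/720) = 1. C is therefore standard normal for any N1. Four million null draws at each interim size agree:

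| N1 | w1 | w2 | P(C > 1.960) | P(C > 1.645) |
|---|---|---|---|---|
| 360 | 0.707 | 0.707 | 0.0249 | 0.0500 |
| 450 | 0.791 | 0.612 | 0.0251 | 0.0500 |
| 540 | 0.866 | 0.500 | 0.0250 | 0.0499 |

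These draws show what each threshold costs. They cannot show which threshold the SAP means, because the threshold is an input. That question is answered by steps 1 and 2.

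**The case for a change.** The best case for acting is that a confirmatory rule should not depend on inference from elsewhere. SAP 5.1.1 does not point to SAP 1.4, and a criterion for counting simulated successes is not formally a decision rule. The Protocol describes no combination test, so it cannot settle the matter directly. The choice could also matter in practice. With the log-logistic scale of 0.5213 and 600 analysed, the chance that a result falls between the two cut-offs is as follows:

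- 25% reduction: 98.8 − 97.4 = 1.4 points (3.2 at the upper-limit scale)
- 17% reduction: 81.1 − 71.5 = 9.6 points
- 13% reduction: 59.64 − 47.17 = 12.5 points

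The last two are the Phase 2 estimates for 600 mg with and without oseltamivir (Protocol 1.1). Both were against placebo and neither was statistically significant, so they serve only as illustrations.

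One figure even leans the other way. The headline 90% power (scale 0.55) does not reproduce at either cut-off: the formula gives 95.9% at 0.025 and 98.0% at 0.05. If the 25% improvement is read as time divided by 1.25, simulation gives 81.5% at 0.025 and 88.9% at 0.05, and the latter is close to 90%.

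Of this, the absence of a number in the decision sentence stands. The rest does not carry the point. The headline match needs a reading that conflicts with the 25% reduction stated in the same section and with the 0.025 criterion printed there. The between-cut-off probabilities measure what would be at stake if two readings were equally tenable, and they are not: a one-sided p between 0.025 and 0.05 plainly fails a two-sided 5% test.

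**Conclusion.** The concern does not hold as a type I error problem. SAP 5.1.1 fixes the level as two-sided 5%, tells the reader that the p-values which follow are one-sided, and leaves the halving to the analyst. SAP 1.4 and Protocol 11.3 carry out that halving for the same Gehan-Wilcoxon test, and the power table confirms it. The rule is then C > 1.960 with a directional error of 2.5%; the 5.0% figure describes a misreading. The section already carries the level to every step of the hierarchy and to both the ITT-i and oseltamivir-subset analyses, so nothing is open there either. Writing 0.025 beside the rule would be harmless, but it would alter no decision the plan leads to.

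This rests on valid, independent stage-wise p-values. The futility rule sits in documents outside the protocol and SAP; a stop for futility could only lower the false-positive rate. The mismatch in the headline 90% power is a separate matter and does not bear on the threshold.
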